Protocol

**TITLE**: Dual benefits of Vaginal Estriol: improved urogenital health and re-myelination in relapsing remitting multiple sclerosis (RRMS)?

INVESTIGATORS:

- 1. [name]
- 2. [name]
- 3. [name]
- 4. [name]
- 5. [name]
- 6. [name], PhD

AIMS:

- 1. To evaluate the efficiency of vaginal estriol, as a treatment for urogenital symptoms in female patients with RRMS.
- 2. To evaluate the potential role of vaginal estriol in re-myelination in RRMS patients.

The goal of this pilot project is to determine the effectiveness of 1 mg transvaginal estriol, as an adjunctive therapy for female MS patients. Our goal is to recruit 20 patients from our MS clinic in the neurology department of Texas Tech University Health Sciences Center. This study has been planned in collaboration with reproductive endocrinology, endocrinology, gynecology and basic science. The 1mg transvaginal dose was chosen after careful search of the literature and consultation with our collaborators.

OBJECTIVES:

- Aim 1: Define if transvaginal estriol improves urogenital symptoms (urgency, frequency, intermittent incontinence), in female patients with Relapsing Remitting MS (RRMS). Bladder control scale, will be given at baseline, 3, 6, and 9 months after starting transvaginal estriol. Quality of life questionnaire will be given at baseline and at 9 months after starting vaginal estriol.
- Aim 2: Assess for evidence of re-myelination associated to the use of transvaginal estriol in woman with MS. Objective measurements for re-myelination will be quantified with brain MRI 3T, Optical coherence tomography (OCT)-and Visual evoked potentials (VEP).

INTRODUCTION / BACKGROUND / SIGNIFICANCE:

More than 2.3 million persons suffer from MS worldwide. Demyelination and axonal loss are the main pathological process in MS. Unfortunately remyelination occurs an incomplete fashion (Mallik, Samson, Wheeler-Kingshott, & Miller, 2014). Experimental models of MS have shown that preservation of myelin and remyelination of axons can increase neuronal survival. Until now, treatment for MS may decrease the relapse rate and progression, without any significant effect on remyelination.

Urinary issues in MS

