- 1. Female patients with RRMS between the ages of 35 to 65.
 - A) Being prescribed vaginal estriol to treat their urogenital symptoms.
 - B) Patients that had underwent menopause or surgical hysterectomy.
- 2. Patients will continue their disease modifying agent for MS during the trial.

Exclusion criteria:

- 1. Patients with personal history of breast cancer, uterine or ovarian cancer.
- 2. Patients with history of fibrocystic breast disease, heart attack or stroke.
- 3. Patients with history of thromboembolism.
- 4. Patients with progressive multiple sclerosis
- 5. Patients who are unable to undergo an MRI
- 6. Males
- 7. Patient is already on vaginal or oral or transdermal estrogens
- 8. Pregnant or breast-feeding patients
- 9. Patient taking sex hormones eg testosterone for libido
- 10. Patients taking DHEA or OTC related products that could influence the hormonal milieu.
- 11. Patient with prolapse uterus or conditions that would impact on transvaginal absorption of estriol

Enrollment in the study will be timed to their follow up brain MRI which will be performed as standard of care. Patients that have no baseline MRI or are unable to undergo MRI will be excluded from the study.

Site of study: The TTUHSC department of Neurology, MS clinic, Lubbock, TX; The TTUHSC Department of Ophthalmology and Visual Sciences, Lubbock, TX

Design:

This is a single-group prospective repeated-measures pilot trial. Duration is 12 months

Intervention:

Estriol vaginal cream will be formulated by Twin Oaks Pharmacy's compounding pharmacy, Regional Pharmacy, by the same compound specialist. 30 mg estriol powder will be mixed with 5 mL of propylene glycol and 22 g of vaginal base cream. The product can be stored at room temperature and has a shelf life of up to 4 months. It comes with an applicator.

The 1 mg dosing was chosen due to evidence in previous trials, and a systematic review of randomized trials comparing vaginal estrogens. It was concluded that the 1mg vaginal estroid, was superior to lower doses for the treatment of urogenital symptoms. (Rahn et al., 2014).

Study visits/Roles of subjects:

Initial visit:

After the informed consent has been obtained and all questions have been addressed Potential participants will be screened to ensure they are eligible for the clinical trial. Once eligibility has

been verified

- 1. Blood will be collected for baseline laboratory studies serum estriol, FSH and LH level. (about 20 ml of blood)

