- 2. Baseline urogenital status will be evaluated by
 - Bladder Control Scale (BLCS) questionnaire
- 3. Multiple Sclerosis Quality of Life-54 (l-54) questionnaire will be completed
- 4. Baseline Visual Evoked Potential (VEP) within 4 weeks of Initial Visit
- 5. Optical Coherence Tomography (OCT) (occurs at the Ophthalmology clinic) within 4 weeks of Initial Visit
- 3 Tesla brain MRI will be performed as well. (within 3 months of initial visit)
- Dispense vaginal estriol cream once all baselines are complete

The primary investigators will instruct how to correctly use vaginal cream. Patients will be instructed to draw 1 mg of estriol vaginal cream with the applicator and apply intravaginally. They will be instructed to lay on their back for 30 min after vaginal cream application once a day for the duration of the study. The applicator is reusable, cleaning technique will also be given to the patient during their visit and reinforced during follow up. The applicator will be washed with regular soap and water and let air dry.

Patients will be instructed not to start applying vaginal cream until baseline lab work and imaging has been performed.

Three-month visit (90 days +/- 10 days):

- BLCS questionnaire will be completed
- Blood will be collected for serum estriol, FSH and LH level. (about 20 ml of blood)
- VEP and OCT will be also performed. ± 3 weeks of 3 month Visit
- Dispense vaginal estriol cream

Six-month visit (180 days +/- 10 days):

- BLCS questionnaire will be completed
- Blood will be collected for serum estriol, FSH and LH level. (about 20 ml of blood)
- VEP and OCT will be also performed. ±-3 weeks of 6 month Visit
- Dispense vaginal estriol cream

Nine-month visit (270 days +/- 10 days-FINAL VISIT):

- BLCS and MSQOL-54 questionnaires will be completed
- Blood will be collected f serum estriol, FSH and LH level. (about 20 ml of blood)
- 3 Tesla brain MRI will be repeated. \pm 3 months of 9 month Visit

During each visit patients will be questioned for adverse events, patients will also have a number to call in case of questions, concerns or adverse events.

Due to the nature of RRMS there might be acute exacerbations in which the patient will be treated with IV methylprednisolone 1gm a day x 3 to 5 days, this is the standard of care for MS exacerbations.

Schedule of events

Procedures	Screening visit	3 month visit	6 month visit	9 month visit FINAL VISIT
Date				
ICF	Х			
1&E	Х			
Blood work	x	x	x	x
BLCS	x	x	x	x
questionnaire				

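### The repeat MRI for Aim 2 may be taken three months either side of the month-9 visit, the end of treatment is contradictory, and no rule separates the resulting scans

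*Combined protocol and SAP*

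**What the plan says.** **Aim 2 measures.** Under Objectives, "Objective measurements for re-myelination will be quantified with brain MRI 3T", together with OCT and VEP. Outcome variables lists DTI, T2 and FLAIR lesions, DWI and T1 black holes.

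**Repeat MRI.** It is listed under the Nine-month visit (day 270 ± 10, labelled the final visit) with a window of plus or minus "3 months of 9 month Visit". The Schedule of events repeats a 3-month window. VEP and OCT are done at baseline, month 3 and month 6, with ±3 weeks at the two later visits, so MRI is the only Aim 2 measure after month 6.

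**Baseline MRI.** "Enrollment in the study will be timed to their follow up brain MRI" (Exclusion criteria), and the scan is "within 3 months of initial visit" (Initial visit). Before or after that visit is not specified. Treatment waits for it: "Dispense vaginal estriol cream once all baselines are complete".

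**Day 0.** Objectives times the bladder questionnaire at "baseline, 3, 6, and 9 months after starting transvaginal estriol". The visit descriptions give day numbers without saying what they are counted from.

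**End of treatment.**
- Cream is applied "once a day for the duration of the study" (Initial visit).
- "Duration is 12 months" (Design).
- The final visit is month 9.
- Cream is last dispensed at month 6, with a shelf life of up to 4 months (Intervention).
- Compliance is last checked at month 9 (Schedule of events).

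**Analysis and reading.** The Analysis section names methods for patient characteristics, blood work, urinary symptoms and quality of life, and none for MRI, VEP or OCT. The MRI reader is independent of the primary investigator. Masking to scan order is not mentioned.

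**The concern.** Each patient is her own control, so the MRI evidence is one difference per patient. That difference has a clear meaning only if the reader knows what interval and how much treatment it covers. Lesion changes can accumulate with calendar time whatever the treatment, while an effect of estriol on DTI would be expected to depend on time on treatment. Followed as written, the plan averages differences over unequal intervals and unequal exposure, possibly including scans taken after treatment has stopped, with no rule to tell them apart.

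There is also a reading bias. A reader who can tell which scan came first may lean toward improvement or worsening. Independence from the investigator does not remove that.

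**Working it through.** Nominal days, 30-day months, 3 months = 90 days. The plan's own timing inputs are day 270 for the final visit, ±90 days for the repeat MRI and 90 days for the baseline MRI.

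**1. Day of the repeat MRI.** 270 − 90 = 180 to 270 + 90 = 360. Adding the ±10-day visit window gives 170 to 370.

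**2. Interval between the two scans.**

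| Day 0 | Baseline scan | Shortest | Longest |
|---|---|---|---|
| First application | 0 to 90 days before day 0 | 180 + 0 = 180 | 360 + 90 = 450 |
| Initial visit | up to 90 days before or after day 0 | 180 − 90 = 90 | 360 + 90 = 450 |

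In the first row the ratio is 450/180 = 2.5. If baseline VEP or OCT (4-week window) delays the start by 28 days, the longest is 478. In the second row the shortest becomes 80 with the visit window.

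**3. Days on treatment at the repeat MRI (day 0 = first application).** If cream stops at day 270, days on treatment = min(scan day, 270), which is 180 to 270, ratio 1.5. Time off treatment is up to 360 − 270 = 90 days. The share of the window after the nominal final visit is (360 − 270)/180 = 0.50.

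For cream to continue to day 360, supply dispensed at about day 180 would have to last 180 days. A 4-month shelf life (about 120 days) ends near day 180 + 120 = 300, and no later dispensing is scheduled.

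**4. Power.** The sample-size section gives d = 0.53 to 0.66 for n = 20, α = 0.05 and power 0.80. The upper end reproduces: a two-sided paired t-test at d = 0.66 has power 0.7995. The lower end is nearly reproduced (d = 0.54) by a four-visit repeated-measures ANOVA with correlation 0.5, which is my assumption.

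Suppose change accrues linearly and scan days are uniform on 180 to 360, that is, accrual does not stop at day 270. Then the SD is 180/√12 = 52 days, CV = 52/270 = 0.19, and effective d = d/√(1 + (CV·d)²).
- d = 0.66: effective d 0.655; power 0.799 becomes 0.793.
- d = 0.53: effective d 0.527; power 0.614 becomes 0.609.

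If accrual stops with cream at day 270, mean days on treatment are 0.5 × 225 + 0.5 × 270 = 247.5. With d = 0.66 at day 270, the mean effect is 0.66 × 247.5/270 = 0.605. Power is then 0.728 with no spread around that mean and 0.726 with it (variance of days 843.75, SD 29). In both cases the spread costs under 1 percentage point. The lower mean exposure matters more, but only under this linear assumption. If the effect plateaus before month 6, neither matters.

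**5. What a time adjustment can support with 20 patients.**
- *Detecting a time trend:* tanh((1.96 + 0.84)/√17) = 0.59, so a correlation of about 0.59 is needed for 80% power.
- *Fitting interval and days on treatment together:* with a uniform gap of 0 to 90 days before treatment, the variance of the gap is 675 and that of time since start is 2700. If cream runs to day 360, r² = 2700/3375 = 0.80 and the variance inflation factor is 1/(1 − 0.80) = 5.0. With a day-270 stop, r² = 1350²/(843.75 × 3375) = 0.64 and the factor is 2.8. Use one term at most.
- *Fitting only on-treatment scans, centred at day 270:* about 10 patients (mean day 225, variance 675). The standard error relative to a simple mean of 20 is √(1/10 + 45²/(9 × 675)) / √(1/20) = 2.9. The main result should therefore keep all patients.

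**The case against.** The strongest reply is that the scans are routine care at no extra cost, so a wide window is the price of having them. Enrolment is timed to the routine scan, which may keep the baseline gap short. The 12 months may simply be the final visit plus the MRI window. Scan dates may already be on the attached data sheet, which is not in the public document. A single-group pilot cannot attribute change to estriol in any case.

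Much of this stands. It explains the window, makes the ranges above limits and not forecasts, and rules out a costly remedy. It does not say whether cream continues after month 9, what the visit days count from, or how late scans are handled. Recorded dates do not help unless they are reported and used.

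A reader might go further in four ways.
- **Exposure varies 2-fold (180 to 360 days).** That needs cream to month 12, which the dispensing schedule and shelf life do not support.
- **Scans after the final visit are off treatment.** This is possible but not established, because no stop day is given.
- **The study loses power.** The spread itself costs under 1 point on the assumptions shown. The stated effect size refers to an unnamed main outcome and to no particular scan day, so the documents support no loss figure for MRI.
- **The missing Aim 2 model is the defect.** In a pilot this alone would be missing detail. It matters here because the scans to be pooled are not alike.

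**Conclusion.** The point holds as a matter of interpretability and bias. The repeat MRI may fall about day 180 to 360. The scan-to-scan interval is about 180 to 450 days if visits run from first application, and could be as short as about 90 days if they run from the initial visit and the baseline scan may follow it. If cream stops at month 9, exposure at the repeat scan varies 1.5-fold, and half of the permitted window lies up to 90 days after treatment. The passages on the end of treatment contradict one another and must be reconciled; the documents do not settle which applies.

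These figures rest on nominal days and on the outer limits of the windows. The actual spread depends on routine booking. The change is worth making because it is cheap and because a clear descriptive before-after change is the most that Aim 2 can deliver.

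**What to change.** 1. Reconcile the passages on study duration, end of treatment and dispensing, and state what day 0 is for the visits.
2. Record the dates of each MRI and of first and last application. Report the mean before-after MRI change in all patients as the main descriptive result, beside the distribution of scan intervals and days on treatment. Add a sensitivity analysis that leaves out, or reports separately, scans after last application.
3. Optionally, for continuous MRI outcomes, add one actual-time term fitted in all patients and centred at its observed mean, so that the intercept stays the mean change. Report it with its confidence interval and not as a test of exposure-response.
4. Where routine booking allows, prefer a repeat MRI that is not after the reconciled end of treatment.
5. Give the existing independent reader each patient's two scans with dates removed and in random order.

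**Cost:** date fields if the data sheet lacks them, some image preparation, and one residual degree of freedom (19 to 18 with 20 patients) if the optional term is used. No added staff, procedures or patients.

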MSQOL-54	x			x
questionnaire				
VEP (4 week	x	x	x	
window for				
screening visit or 3				
week window for 3				
and 6 month visits)				
OCT (4 week	x	x	x	
window for				
screening visit or 3				
week window for 3				
and 6 month visits))				
MRI variables (3	x			X
month window)				
Vaginal cream	x			
instructions				
Vaginal cream	х	x	x	
dispensing (once				
baselines				
complete)				
Compliance of		x	x	x
vaginal cream use				

Materials, instruments or measurements:

Urogenital measurements:

- Bladder control scale (BLCS) questionnaire (validated and used for evaluation of MS bladder symptoms. {Turnbull et al, 1992}). Raw scores on the 4 items are summed to create a Bladder Control Scale (BLCS) total score. Scores can range from 0-22, with higher scores indicating greater bladder control problems. See attached document. TEXAS TECH UNIVERSITY HEALTH SCIENCES CENTER

Quality of life:

- Quality of life questionnaire (Multple Sclerosis Quality of Life-54 {MSQOL-54}. Validated and widely used for MS patients. (Vickrey et al, 1995) (Vickrey et al, 1997). The questionnaire includes 54 questions that provide scores on physical and mental health status. Both scores can range 0-100. See attached document.

Blood work:

Levels of estriol, FSH, LH will be performed in Texas Tech Health Science Laboratory ([name] certified lab). The assay used will be the Beckman Coulter Access 2 immunoassay system analyzer. This will be run by an established OB/GYN hormone laboratory under the supervision of [name] and [name].

Re-myelinating measurements:

• Visual evoked potential (VEP) (measurement of the electrical signal recorded at the scalp over the occipital cortex in response to light stimulus) VEP/Prolongation of the P100 latency, is an indirect tool for remyelination in MS. (The test is non-invasive, patients will be looking at a checkboard pattern while the technician is measuring the time it takes to register the image to the brain cortex. This is achieved with scalp electrode in the posterior region.)

• 3Tesla brain MRI (performed as standard of care with no extra cost) will be evaluated for possible changes in white matter lesions, and Diffusion Tensor Imaging (DTI). This will be read by an expert MD collaborator independent from primary investigator.

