• Optical coherence tomography (OCT) (noninvasive scan of the retinal layer which provides morphology imagery of the ganglion cell layer which is frequently affected in MS) (Noninvasive test, duration of about 5 to 10 min to perform, patient has to stay still and focus on a small light while we take a picture of the retina layer with the device.)

Data Sheet: A spreadsheet is attached. We will be gathering demographic data, MRI information, EDSS score, and electrophysiologic information, for details please see the spreadsheet attached.

Outcome variables:

1- Urogenital symptoms such as frequency, incontinence, frequent urinary tract infections, and BLCS questionnaire scores.

2- Remyelination (measured by brain MRI 3 DTI, other measurements include presence of T2 lesions, Flair lesions, DWI, T1 black hole, and DTI; Optical coherence tomography (OCT); and visual evoked potentials (VEP).

3- Quality of life, assessed using MSQOL-54 questionnaire.

Analysis:

Patient characteristics will be summarized using frequency (percentage) for categorical variables, and mean (SD) or median (interquartile range) for numerical variables as appropriate. Changes in blood work variables during the course of the study will be assessed using one-way repeated-measures analysis of variance (ANOVA). Compliance assessments will be used as covariate to adjust the differences if necessary, using an analysis of covariance model (ANCOVA). Urinary symptoms, and quality of life data will be analyzed using mixed-effects linear or logistic regression models for continuous or binary outcomes respectively. These models will account for the effect of estriol over time, compliance with treatment, and relevant patient characteristics.

Justification for Sample size:

This is a pilot study. We are planning to include 20 patients. Each patient will be their own control in a single-group repeated measures design. Assuming a significance level $\alpha = 0.05$, and power 1- $\beta = 0.80$, a

TEXAS TECH UNIVERSITY HEALTH SCIENCES CENTER IRB NUMBER: L19-020 IRB APPROVAL DATE: 12/13/2019

sensitivity power analysis determined that a moderate effect size (d=0.53 to d=0.66) would be required to detect statistically significant changes in the main outcome.

Risks

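### Low-cost improvement: the supplied text does not say that the MRI reader is masked to scan date or order, although scan order is treatment status in this single-group trial.

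*Combined protocol and SAP*

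**What the plan says.** The Design section states: "This is a single-group prospective repeated-measures pilot trial". The sample size section adds: "Each patient will be their own control in a single-group repeated measures design".

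The timing of the scans comes from the study visits. At the initial visit: "Patients will be instructed not to start applying vaginal cream until baseline lab work and imaging has been performed". At the nine-month visit: "3 Tesla brain MRI will be repeated", with a window of 3 months either side. The schedule of events shows no other MRI. The scans are routine clinical ones: "Enrollment in the study will be timed to their follow up brain MRI which will be performed as standard of care".

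The MRI entry under re-myelinating measurements has the scans assessed for change in white matter lesions and for DTI. Its one safeguard is: "This will be read by an expert MD collaborator independent from primary investigator". The Outcome variables section lists "Remyelination (measured by brain MRI 3 DTI, other measurements include presence of T2 lesions, Flair lesions, DWI, T1 black hole, and DTI", followed by OCT and VEP. Aim 2 describes the remyelination measurements as objective.

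Two other places bear on the point. The Confidentiality section says that patient information will be de-identified. The Data Sheet paragraph refers to an attached spreadsheet for details of the data collected, MRI information included; that attachment is not in the supplied text.

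**The concern.** With no control group, the MRI evidence for Aim 2 is a within-patient change from the first scan to the second. In every patient the first scan precedes the cream and the second follows its start, so a reader who can see dates or order knows treatment status for every image. Independence from the primary investigator does not hide this.

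Some of the listed measures need judgement: white matter lesions, T2 and FLAIR lesions, and T1 black holes. If the reader expects improvement, that expectation can enter the change score directly, and no comparison arm read by the same person would cancel it. Masked reading is what would support calling these particular measures objective. A later analysis of scores made with the order known cannot remove the effect.

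**Working it through.** **Step 1. Is scan order the same thing as treatment status?** Set side by side, the initial-visit instruction puts the baseline MRI before any cream, and the nine-month visit supplies the only repeat. There is one group. Order therefore identifies untreated and post-start scans in all patients.

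**Step 2. Is order hidden from the reader?**
- The re-myelinating measurements section gives independence from the primary investigator. An independent reader may still see dates and know the hypothesis.
- The Confidentiality section protects patient identity. It does not mention scan date, visit label or order.
- The scans are standard-of-care scans, and no step removes their dates.
- The attached spreadsheet was not supplied.

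So the supplied text does not state masking. It does not state that the reading is unmasked either.

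**Step 3. Which measures are exposed?** Mainly the judged lesion measures. DTI is exposed only if regions are placed by hand, which the documents do not say. VEP and OCT are outside this point.

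**Step 4. How large could the effect be?** The documents give no figure, and the Analysis section names no test for MRI. The following is an illustration on assumed inputs.

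Inputs from the plan: n = 20, significance level 0.05, power 0.80, and a detectable effect of d = 0.53 to 0.66. Assumed: a two-sided paired t-test, no true change, and a shift δ in the mean change caused by expectation, in units of the SD of the change.

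Formula: the critical value is t(0.975; 19 df) = 2.093, the noncentrality is δ√20, and P(positive) = P(|T| > 2.093), where T is noncentral t with 19 df.

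Check against the plan's own figure: at δ = 0.66 the noncentrality is 0.66 × 4.472 = 2.95 and P = 79.9%. This reproduces the upper end of the stated range at 80% power. The lower end is not needed here. It is approached (0.54 against 0.53) only by assuming a four-visit repeated-measures ANOVA with within-patient correlation 0.5 and d taken as 2f, whereas MRI has two time points.

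| Assumed shift δ (SD of change) | Noncentrality δ√20 | Favourable | Unfavourable | Positive test, either direction |
|---|---|---|---|---|
| 0 | 0 | 2.5% | 2.5% | 5.0% |
| 0.1 | 0.447 | 6.2% | 0.9% | 7.1% |
| 0.2 | 0.894 | 13.3% | 0.2% | 13.6% |
| 0.3 | 1.342 | 24.6% | 0.1% | 24.7% |

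(Components may differ from totals by rounding.) If the MRI change is only described and not tested, the estimate is still displaced by δ.

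**The case against.** **The gap may not be real.** The missing spreadsheet could hold a reading procedure. This stands, and it limits the claim to what the supplied text states. The attachment is described as a data-collection sheet, however, and if masking is already practised one sentence in the protocol would settle the matter.

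**The mechanism is conditional.** It needs a reader who knows the order, knows the patient is on estriol, and expects benefit. The plan says none of this, and independence is a partial safeguard. This also stands; the direction and size of any shift are assumptions.

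**The numbers rest on a test that the plan does not contain, and small shifts matter little.** Both parts are correct. At 0.1 SD the rate is 7.1%. With a yes/no lesion score and an exact McNemar test, assuming 10% to 20% chance disagreement each way, moving a further 10% of patients to better gives 4.6% to 5.0%, no more than nominal (against 0.5% to 1.9% with no shift). The larger rates need the larger assumed shifts.

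**Masking may be imperfect.** Recall or new lesions can reveal the order. That reduces the gain but does not remove it. If the shift follows the reader's guess and 75% of guesses are right, the average shift in the 0.3 SD case is 0.3 × (0.75 − 0.25) = 0.15 SD, and by simulation the 24.7% falls to 9.6%.

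**It is a small uncontrolled pilot, and masking will not make a change attributable to estriol.** True. A reader might infer that masked reading would make the MRI result evidence of a treatment effect. It would not: time, the disease-modifying agents that patients continue, and possible steroid courses for exacerbations stay mixed with any effect. What remains is one avoidable source of bias in a stated aim, with an inexpensive remedy.

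**Conclusion.** The point holds as a low-cost improvement. The supplied text gives the MRI reader's independence but does not state masking to scan date or order, in a design where order identifies treatment status in every patient. The exposure is in the judged lesion measures, and in DTI only if regions are hand-placed.

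Its size is unknown. The rates of 7.1%, 13.6% and 24.7% rest on assumed shifts of 0.1, 0.2 and 0.3 SD, on no true change and on a paired t-test that the plan does not specify.

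Two stronger readings are tempting and are not supported. One is that the MRI reading is known to be unmasked; the documents are silent, and an attachment is missing. The other is that the trial's false-positive rate for MRI is raised to a particular level; no document gives a size for reader expectation or a test to which such a rate would apply.

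**What to change.** In the section on re-myelinating measurements, after the sentence on the expert reader, add:

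> For the research reading, the same reader will assess each patient's two scans together after the second scan, with dates and visit labels removed and in random order. Any DTI regions placed by hand will be placed in this session. An existing team member other than the reader holds the order list, and scores are locked before the order is revealed. Dated clinical reports are kept separate.

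If the spreadsheet already contains such a procedure, a cross-reference to it is enough.

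**Cost.** At most about 40 readings (20 patients × 2 scans) by the existing reader, and few or none extra if the reading already described is the research reading; plus some file preparation. No new assessor, patient, scan or visit. The documents give no costs, so calling this cheap is a judgement.

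**Downside.** MRI results wait until the second scan is available.

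### Blood work is analysed by repeated-measures ANOVA, which usually needs all four draws, while the bladder score from the same visits gets a mixed model that keeps partial records; no reason and no missing-data rule is given (low priority)

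*Combined protocol and SAP*

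**What the plan says.** The Analysis section names two methods for repeated measurements on the same women.

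- Hormones: "Changes in blood work variables during the course of the study will be assessed using one-way repeated-measures analysis of variance (ANOVA"). A compliance adjustment by ANCOVA may be added if needed.
- Bladder and quality-of-life data: "Urinary symptoms, and quality of life data will be analyzed using mixed-effects linear or logistic regression models". These models also carry time, compliance and patient characteristics.

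The visit descriptions and the Schedule of events place the hormone draws at baseline and at 3, 6 and 9 months. The follow-up text reads "Blood will be collected for serum estriol, FSH and LH level". BLCS is completed at the same four visits. MSQOL-54 is completed only at baseline and month 9.

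On numbers, the sample size section says "We are planning to include 20 patients" and "Each patient will be their own control in a single-group repeated measures design". It makes no allowance for dropout. No section defines an analysis set or says how a missed draw or a withdrawal is handled. The Outcome variables list has three entries (urogenital symptoms, remyelination, quality of life), and the hormones are not among them.

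**The concern.** Classical one-way repeated-measures ANOVA works on a full row of values per woman. A woman who leaves after month 6, or misses a single draw, would normally be left out altogether, and her valid earlier values would go with her. The same woman stays in the BLCS model with whatever visits she completed. Because the plan has no missing-data rule, the choice of method and software decides by default who is analysed.

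Two things are at stake. The first is precision, in a trial of 20 women. The second is representativeness. A complete-case analysis is in general unbiased only if the women with all four draws resemble the rest, whereas a mixed model relies on the weaker assumption that missingness depends only on observed values. Women who stop the cream or miss visits may plausibly differ in exposure, and serum estriol is the trial's only direct measure of systemic exposure. The documents give nothing from which to size such a bias, so the check below deals with precision.

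**Working it through.** **1. The plan's own figure.** The sample size section says that a "moderate effect size (d=0.53 to d=0.66) would be required to detect statistically significant changes in the main outcome". With n = 20, alpha 0.05 and power 0.80:

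- a two-sided paired t test gives d = 0.660, the upper end;
- a one-group repeated-measures F test with 4 occasions, correlation 0.5 (assumed) and d = 2f gives d = 0.540, and power at d = 0.53 is 0.783, close to the lower end.

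The stated range therefore fits 20 women with complete data. It concerns the main outcome, not the hormones, and it leaves no slack for missing values.

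**2. What the methods do with gaps.** In one simulated data set of 20 women, 4 were incomplete and 75 of 80 values were present. The standard repeated-measures ANOVA routine refused the unbalanced data and ran only on 16 women (64 values). A mixed model used 20 women and 75 values. An ANOVA fitted as a linear model with woman and visit as factors also used all 75. In that single data set the reported standard errors were nearly equal (0.292 against 0.289 to 0.294), because the residual variance was estimated differently in the two subsets. The comparison below therefore uses expected standard errors at a common variance.

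**3. Inputs for the comparison.** N = 20 and four draws come from the documents. The missingness rates, equal correlation between visits (0.3 to 0.7), known variance, and a baseline draw for every woman are assumptions. Standard errors are for change from baseline, in units of the between-woman SD. The complete-case SE is sqrt(2(1 − rho)/n_c), where n_c is the number of women with all four draws. The mixed-model SE is the generalised-least-squares value over all observed patterns.

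**4. Draws missing independently.** Here n_c = 20 × (1 − p)^3.

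| p per post-baseline draw | n_c | Complete-case SE (rho 0.5) | Mixed-model SE (rho 0.5) | Ratio, rho 0.3 to 0.7 |
|---|---|---|---|---|
| 5% | 20 × 0.857 = 17.1 | 0.2415 | 0.2273 | 1.06 |
| 10% | 20 × 0.729 = 14.6 | 0.2619 | 0.2313 | 1.13 |

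The ratio is the same at months 3, 6 and 9. As a rough check, using only the women with both baseline and the visit in question leaves 19 or 18, so the ratio would be sqrt(19/17.1) = 1.05 or sqrt(18/14.6) = 1.11. The mixed model does slightly better than that.

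**5. 20% withdraw between months 6 and 9.** Four women leave, so n_c = 16.

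- Months 3 and 6: all 20 values exist, so the ratio is sqrt(20/16) = 1.12.
- Month 9, rho 0.5: the coefficient of month 9 on each of the three earlier values is rho/(1 + 2·rho) = 0.25, and the residual variance is 1 − 3·rho²/(1 + 2·rho) = 0.625. The total variance of the change is 2(1 − rho) = 1, so 0.375 is carried by the earlier visits. The mixed-model variance is 0.625/16 + 0.375/20 = 0.0578, giving SE 0.240. The complete-case variance is 1/16 = 0.0625, giving SE 0.250. The ratio is 0.250/0.240 = 1.04, and it stays at 1.04 for rho 0.3 and 0.7.

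**6. Quality of life for comparison.** With two occasions and 4 of 20 women lacking month 9, the mixed-model SE of change is 0.96 to 0.98 of the complete-case SE. The contrast between methods therefore rests on BLCS, not on MSQOL-54.

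**The case against.** The strongest reply is that the plan does not say what a reader might infer from it. There is no rule that drops women. Complete-case analysis is the usual behaviour of the method, and an ANOVA fitted as a linear model would keep every draw. That stands, but it leaves the plan open to either reading, which is a reason to settle it.

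The hormones are also outside the aims and the three listed outcomes, so no conclusion on bladder symptoms, remyelination or quality of life depends on this ANOVA. That stands and sets the priority.

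Three stronger readings are tempting and fail.

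- One could compare complete cases with 20 fully observed women and report losses of 8% (sqrt(20/17.1) = 1.08) and 17% (sqrt(20/14.6) = 1.17), or 12% at every visit under withdrawal. The mixed model also loses precision when draws are missing, so only the difference between the two methods is avoidable.
- One could say that exposure and bladder response can no longer be read in the same patients. Women with all four draws would normally be a subset of those in the BLCS analysis, so both can be read there, and no exposure-response analysis is planned.
- One could extend the contrast to quality of life. A woman who leaves early has only a baseline MSQOL-54 score and adds almost nothing on change.

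Finally, compliance is a term in the planned mixed models and is recorded only at 3, 6 and 9 months. A missed visit may therefore lack that covariate too, which narrows the difference somewhat.

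**Conclusion.** The inconsistency is real but minor. Two measures taken from the same women at the same four visits get different methods without a stated reason. The one named for the hormones would by default discard partial records, and nothing in the plan says otherwise.

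The avoidable loss is about 6% or 13% in standard error at 5% or 10% missing per post-baseline draw. With 20% withdrawal between months 6 and 9 it is about 12% at months 3 and 6 and about 4% at month 9. These sizes rest on assumed missingness, equal correlation of 0.3 to 0.7 and complete-case use of the ANOVA. If no draw is missed, the loss is zero. The documents support neither a claim that the plan excludes women by rule nor a claim that its efficacy conclusions are at risk. Low priority.

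**What to change.** In the Analysis section, replace the blood-work ANOVA with a linear mixed model for each hormone:

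- visit (baseline, 3, 6, 9 months) as a categorical effect and patient as a random effect;
- log scale for estriol if it is skewed;
- every available draw used, with the missing-data assumption stated;
- a small-sample degrees-of-freedom correction such as Kenward-Roger;
- the number of women contributing reported at each visit.

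The cost is one or two sentences and no new data, since the plan already uses this model type for urinary symptoms. With complete, balanced data a random-intercept model gives essentially the ANOVA result.

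There is a small downside. The random-intercept model assumes equal correlation between visits, and inference with 20 women needs the small-sample correction. The change should not be presented as giving exactly the same women as the BLCS analysis at every visit, because a woman may complete the questionnaire and miss the draw. The reported counts make any difference visible.
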